6.8 Treatment exposure and compliance

Pharmacokinetic data and parameters (measures of treatment exposure) will be determined in all subjects treated with CFZ533, as detailed in [Section 8.7](#).

6.9 Recommended treatment of adverse events

Parenteral administration of monoclonal antibodies can be associated with acute, severe reactions (occurring within the first few hours post dose) secondary to hypersensitivity, immunogenicity, or ADCC-mediated cell depletion.

In this study, CFZ533 will be administered as intravenous infusion. No infusion reactions have been noted in the Phase 1 and Phase 2 clinical program with CFZ533 so far; however, investigators should be aware of the possibility and be prepared to treat such events.

Subjects will be monitored at the site for at least 1 hour post dose or longer, at the discretion of the Investigator, to ensure adequate safety monitoring. In case of any signs of an acute reaction, clinical treatment will be provided as determined by the treating physician on a case-by-case basis and depending on the severity, using symptomatic treatment, anti-histamines, Nonsteroidal anti-inflammatory drugs (NSAIDs), acetaminophen, intravenous fluids, corticosteroids, or adrenaline.

For the severity evaluation of allergic reaction, anaphylaxis and cytokine release and any other adverse event which may potentially lead to treatment discontinuation, it is recommended to follow the guidelines by the National Cancer Institute Common Toxicity Criteria version 4.03 ([NCI-CTCAE 2010](#)).

Use of rescue medication must be recorded on the Concomitant medications / Significant non-drug therapies eCRF after start of study drug.

6.10 Rescue medication

Standard of care treatment for lupus nephritis includes conventional immunomodulatory therapy (e.g. antimalarials), non-steroidal anti-inflammatory drugs, and immuno-suppressive agents such as corticosteroids, cyclophosphamide, calcineurin inhibitors, mycophenolate, or azathioprine. B cell depleting agent rituximab is also used for certain cases. Medication for SLE is similar, but often including further immunosuppressives such as methotrexate, and recently, also the anti-BAFF monoclonal antibody, belimumab.

In case of severe, clinically significant flare of nephritis or any other SLE manifestations (based on investigator's judgment), introduction or dose increase of any standard of care therapies (e.g. corticosteroids) will be at the discretion of the treating physician. Rescue medicine is to be provided by the study center or personal physician. Use of rescue medication (after start of CFZ533 or placebo) must be recorded in the eCRF at the Concomitant medications/Significant non-drug therapies section.

6.11 Concomitant treatment

Certain standard of care therapies (corticosteroids, mycophenolate, azathioprine, methotrexate, antimalarials) in a stable dose are permitted, while others like cyclophosphamide, rituximab, belimumab, calcineurin inhibitors [For China, Hong Kong, and Korea only: (except tacrolimus ≤ 3 mg/day)] are prohibited, as defined in the eligibility criteria. Corticosteroids and antimalarials may be combined with maximum one further permitted standard of care medication (as listed above), to minimize the risk of over-immunosuppression.

Commercially Confidential Information

The Investigator must instruct the subject to notify the study site about any new medications he/she takes after the subject was enrolled into the study.

All prescription medications, over-the-counter drugs and significant non-drug therapies (including physical therapy and blood transfusions) administered or taken within the timeframe defined in the entry criteria prior to the start of the study and during the study, must be recorded on the Concomitant medications/Significant non-drug therapies CRF.

Medication entries should be specific to trade name, the single dose and unit, the frequency and route of administration, the start and discontinuation date and the reason for therapy.

Each concomitant drug must be individually assessed against all exclusion criteria/prohibited medication. If in doubt, the Investigator should contact Novartis before randomizing a subject or, if the subject is already enrolled, to determine if the subject should continue participation in the study.

7 Study completion and discontinuation

7.1 Study completion and post-study treatment

Each subject will be required to complete the study in its entirety and thereafter no further study treatment will be made available to them.

Study completion is defined as when the last subject completes their Study Completion visit, and any repeat assessments associated with this visit have been documented and followed-up

appropriately by the Investigator, or in the event of an early study termination decision, the date of that decision.

If discontinuation of study treatment occurs, the investigator must determine the primary reason for the subject's premature discontinuation of study treatment and record this information on the Dosage Administration CRF. The investigator must also contact the IRT to register the subject's discontinuation from study treatment.

Patients who discontinue study treatment are to continue their study participation, and to complete all study visits.

Patients who decide they do not wish to participate in the study further should NOT be considered withdrawn from the study UNLESS they withdraw their consent. If they fail to return for the study visits for unknown reasons, every effort (e.g. telephone, e-mail, letter) should be made to contact the subject. This contact should preferably be done according to the study visit schedule.

The following data should be collected at minimum via telephone/email contact:

- new / concomitant treatments
- adverse events/Serious Adverse Events

Any unresolved AEs will be followed with additional post-study visits as determined appropriate by the study site investigator and sponsor.

Patients who discontinue the study must be reminded not to become pregnant for 14 weeks after the last dose of study medication.

7.3 Withdrawal of informed consent

Subjects may voluntarily withdraw consent to participate in the study for any reason at any time. Withdrawal of consent occurs only when a subject:

- Does not want to participate in the study anymore, and
- Does not allow further collection of personal data

In this situation, the investigator should make a reasonable effort (e.g. telephone, e-mail, letter) to understand the primary reason for the subject's decision to withdraw his/her consent and record this information.

Study treatment must be discontinued and no further assessments conducted, and the data that would have been collected at subsequent visits will be considered missing.

Further attempts to contact the subject are not allowed unless safety findings require communicating or follow-up.

All efforts should be made to complete the assessments prior to study withdrawal. A final evaluation at the time of the subject's study withdrawal should be made as detailed in the [Assessment table](#).

Novartis will continue to keep and use collected study information (including any data resulting from the analysis of a subject's samples until their time of withdrawal) according to applicable law.

For US: All biological samples not yet analyzed at the time of withdrawal may still be used for further testing/analysis in accordance with the terms of this protocol and of the informed consent form.

For EU and ROW: All biological samples not yet analyzed at the time of withdrawal will no longer be used, unless permitted by applicable law. They will be stored according to applicable legal requirements.

7.4 Lost to follow-up

For subjects whose status is unclear because they fail to appear for study visits without stating an intention to discontinue or withdraw, the investigator should show "due diligence" by documenting in the source documents steps taken to contact the subject, e.g. dates of telephone calls, registered letters, etc. A subject cannot be formally considered lost to follow-up until his/her scheduled end of study visit would have occurred.

7.5 Study stopping rules

Stopping Rules

The study can be terminated at any time for any reason by Novartis. Should this be necessary, the patient should be seen as soon as possible and treated as a prematurely withdrawn subject. The investigator may be informed of additional procedures to be followed in order to ensure that adequate consideration is given to the protection of the patient's interests. The investigator will be responsible for informing IRBs and/or ECs of the early termination of the trial. The study will be paused with no further dosing, and recruitment on hold, pending full safety review if patient(s) experience(s) the following events if related to treatment of CFZ533:

1. One (1) patient with CFZ533-related death
2. Three (3) or more patients with a serious adverse event that is suspected to be related to CFZ533 by the Investigator
3. One (1) patient presenting with suspected CFZ533-related cytokine release syndrome,
4. One (1) patient presenting with a suspected CFZ533-related thromboembolic event that is at least of moderate severity
5. More than one (1) patient with allergic reaction of CTCAE Grade 3 or higher severity
6. Any treatment-related, CTCAE Grade 3 or higher adverse event Criteria considered drug related by the Investigator with the following exceptions:
 - Events not requiring treatment, and diagnostic procedures involving elective or non-urgent hospital admission,
 - Disease Specific Events due to the patients underlying LN diagnosis,
 - AEs/SAEs unrelated to the experimental compound as determined by the Investigator or Novartis
7. Two (2) or more patients presenting with:
 - Progressive renal insufficiency or acute kidney injury defined as a Grade 2 increase in serum creatinine ($1.5 \times \text{ULN}$) in the setting of euvoolemia at any time during the study related to CFZ533
 - Emergent hypogammaglobulinemia defined as total serum IgG below 5.65 g/L or IgM below 0.40 g/L and a reduction in total serum IgG or IgM concentration by 50% or more from baseline, considered clinically significant by the investigator
 - Severe systemic infection or severe opportunistic infection that requires treatment, e.g., sepsis, urosepsis, mycoses, pneumonia.

8. Clinically significant (according to the Investigator) and study drug-related, persisting changes from baseline in vital signs, electrocardiograms, or relevant, persistent changes in laboratory parameters, which are not consistent with existing co-morbidities, in more than one (1) subject within the first 5 treated patients or an incidence of >20% thereafter.
9. Other clinically significant changes or effects in the opinion of the Sponsor that are deemed unsafe to continue dosing.

In addition, all blinded safety data, including disease specific events, will be evaluated by the Sponsor continuously. The study may be paused pending further data analysis and the decision to adjust the dose or modify the medication if the following criteria occur:

- The Sponsor considers that the number and/or severity of AEs justify discontinuation of the study.
- Other clinically significant changes or effects in the opinion of Sponsor that are deemed unsafe to continue dosing.

Furthermore, a Data Monitoring Committee will be established to monitor safety and based on their recommendation the study may be put on hold or modified.

7.6 Early study termination by the sponsor

The study can be terminated by Novartis at any time for any reason. This may include reasons related to the benefit/ risk assessment of participating in the study, practical reasons (including slow enrollment), or for regulatory or medical reasons. Should this be necessary, subjects must be seen as soon as possible and treated as a prematurely discontinued subject. The investigator may be informed of additional procedures to be followed in order to ensure that adequate consideration is given to the protection of the subject's interests. The investigator will be responsible for informing IRBs/IECs of the early termination of the trial.

8 Procedures and assessments

8.1 Assessment schedule

Subjects should be seen for all visits/assessments as outlined in the assessment schedule or as close to the designated day/time as possible.

Missed or rescheduled visits should not lead to automatic discontinuation. Subjects who prematurely discontinue the study drug for any reason should be continuing their study participation, i.e., to complete all study visits.

If an epidemic or pandemic (e.g. COVID-19 pandemic) limits or prevents on-site study visits, alternative methods of providing continuing care may be implemented. Phone calls, virtual contacts (e.g. teleconsult) or visits by site staff to the participant's home depending on local regulations and capabilities, can replace on-site study visits, for the duration of the pandemic until it is safe for the participant to visit the site again.

Table 8-1 Assessment schedule

Epoch	Screening		Treatment								Follow Up					
Visit Name	SCR	BL	Treatment								Follow Up				EOS	
Visit Numbers	1	2	101	102	103	104	105	106	199	201	202	203	204	205	206	299
Week	-4 to -1		1	3	5	9	13	17	21	25	29	33	37	41	45	49
Day	-28 to -8	-7 to -3	1	15 ±1	29 ±2	57 ±2	85 ±2	113 ±2	141 ±2	169 ±3	197 ±3	225 ±3	253 ±3	281 ±3	309 ±3	337 +3
Pre/Post ¹			Pre	Post	Pre	Post	Pre	Post	Pre	Post	Pre	Post	Pre	Post		
Informed consent	X															
Genetic consent	X															
Eligibility criteria	X	X														
Medical history/current conditions	X															
Demography	X															
Body height	X															
Body weight	X	X	X	X	X	X	X	X	X	X	X	X	X	X	X	X
Body temperature	X	X	X	X	X	X	X	X	X	X	X	X	X	X	X	X
Blood pressure/pulse rate	X	X	X	X	X	X	X	X	X	X	X	X	X	X	X	X
Physical examination	X	X	X	X	X	X	X	X	X	X	X	X	X	X	X	X
Electrocardiogram	X	X	X	X	X	X	X	X	X	X	X	X	X	X	X	X

Commercially Confidential Information

Hematology/Clinical Chemistry/ Urinanalysis ⁹	X	X	X	X	X	X	X	X	X	X	X	X	X	X	X	X
Hepatitis, CMV, HIV screen	X ²		X ⁸		X ⁸											
TB screen	X															
FSH ³	X															
Pregnancy test ³	X	X	X	X	X	X	X	X	X	X	X	X	X	X	X	X
ESR, CRP	X	X		X	X	X	X	X	X	X	X	X	X	X	X	X
IgG, IgM	X	X			X			X				X		X		X
C3, C4 Complement	X	X			X			X				X		X		X
Lupus anticoagulant	X		X								X					X
Coagulation test	X	X		X	X	X	X	X	X	X	X	X	X	X	X	X
PK collection ¹			X	X		X	X		X	X	X	X	X	X	X	X
PD collection (total soluble CD40)			X		X				X				X		X	X
Immunogenicity			X		X			X		X		X		X		X

Commercially Confidential Information

Drug administration		X	X	X	X	X	X	X	X							
Study completion																X
Concomitant meds/Therapies										As required						
Adverse Events										As required						
Comments										As required						

¹ Pre-dose collection: ahead of drug administration; post-dose collection: 1h AFTER completion of the i.v. infusion

² HIV and Hepatitis results to be available in Source data, will not be recorded within the eCRF

³ FSH level and serum pregnancy test at Visit 1 for female subjects, all other visits pregnancy test in urine (if FSH ≤ 20)

Commercially Confidential Information

⁸ CMV IgG, IgM and DNA (by PCR) done for all subjects. Hepatitis B monitoring done in subjects with positive serology for anti-HBc at screening (results to be available in Source data, will not be recorded within the eCRF). .

⁹ A first morning void urine sample will be collected in the patients' home and a second spot urine sample will be collected at the investigational site for the analysis of UPCR, albumin, and creatinine.

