Study treatment	
 CFZ533 150 mg or placebo Liquid in vial for injection 
 CFZ533 10 mg/kg administered by intravenous infusion placebo administered by intravenous infusion 
Intravenous infusion will be administered at Days 1, 15, 29, 57, 85, 113, and 141

Pharmacokinetic assessments	
 Free CFZ533 in plasma
Efficacy/PD assessments	
 Urinary protein creatinine ratio (UPCR) Total soluble CD40 (target engagement) in plasma
Key safety assessments	
 Adverse events/Serious adverse events Vital signs ECG evaluation Standard hematology and chemistry evaluations Immunogenicity
Other assessments	Commercially Confidential Information

Data analysis	
The primary variable is the ratio from baseline in urinary protein creatinine ratio (UPCR) at Week 25, using first morning void. This ratio will be log transformed prior to the analysis. A repeated measures mixed model will be fitted with factors for treatment group (CFZ533 or placebo) and visit (e.g. Week 5, 9, 13 etc.). The model will also include a factor for the prednisone dose-equivalent at baseline (≤ 10 mg, >10 mg), which is a stratification factor for the randomization. Log-transformed baseline UPCR will be included in the model as a covariate along with the interactions between visit and all of the fixed effects. A normal errors model will be assumed with an unstructured covariance matrix to account for the correlation within subjects.
 
At each of the visits, the difference between the CFZ533 and placebo group will be estimated (along with its corresponding 95% confidence interval) and then back-transformed to provide an estimate of the ratio between treatment groups.
 
Descriptive statistics will be provided for the safety data (e.g. AEs, vital signs, ECGs, hematology and chemistry evaluations etc.). For serious adverse events and adverse events of special interest, statistical analyses comparing the event rates in the two treatment groups will be performed.

Key words	CFZ533, anti-CD40, moderately active lupus nephritis

1 Introduction

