3.6.3 Blood sample volumes

A maximum of 650 mL of blood is planned to be collected over a period of 53 weeks from each subject as part of the study. Additional samples may be required for safety monitoring.

Timings of blood sample collection are outlined in the [Assessment schedule](#) (Section 8.1).

A summary blood log is provided in the Site Operations Manual (SOM). Instructions for all sample collection, processing, storage and shipment information is also available in the SOM and central Laboratory Manual.

Commercially Confidential Information

4 Population

The study population will be comprised of female and male subjects (in the age range of 18 to 75 years) with moderately active lupus nephritis who are on a stable dose of immunosuppressive treatment and demonstrate moderate disease activity despite standard of care therapy. Moderate disease activity is defined as having clinical signs of renal disease activity such as proteinuria (≥ 0.5) but without an immediate need for induction therapy or for whom standard induction therapy with high dose corticosteroids and mycophenolate or cyclophosphamide is not an option. A total of approximately 60 subjects will be randomized (2:1 ratio active:placebo) to participate in the study.

The Investigator must ensure that all subjects being considered for participation in the study will meet the following eligibility criteria. No additional criteria should be applied by the Investigator, in order that the study population will be representative of all eligible subjects.

Subject selection is to be established by checking through all inclusion and exclusion criteria at screening and baseline. A relevant record (e.g., checklist) of the eligibility criteria must be filed with the subject's source documentation at the study site.

Deviation from any eligibility criterion excludes a subject from enrollment into the study, and randomization to study treatment.

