14. Women of child-bearing potential (defined as all women physiologically capable of becoming pregnant) must use highly effective methods of contraception before entering the study, during dosing and until study completion.

Highly effective contraception methods include:

- Total abstinence from heterosexual intercourse (when this is in line with the preferred and usual lifestyle of the subject). Periodic abstinence (e.g. calendar, ovulation, symptothermal, post-ovulation methods) and withdrawal are not acceptable methods of contraception.
- Female sterilization (have had surgical bilateral oophorectomy with or without hysterectomy), total hysterectomy or tubal ligation at least six weeks before taking

investigational drug. In case of oophorectomy alone, only when the reproductive status of the woman has been confirmed by follow up hormone level assessment.

- Male-partner sterilization (at least 6 months prior to screening). For female subjects in the study, the vasectomized male partner should be the sole partner for that subject.
- Use of oral, injected or implanted hormonal methods of contraception or placement of an intrauterine device (IUD) or intrauterine system (IUS) or other forms of hormonal contraception that have comparable efficacy (failure rate < 1%), for example hormone vaginal ring or transdermal hormone contraception. Women should have been stable on their chosen method of OC for a minimum of 3 months before entering the trial.
- Postmenopausal females must have had no regular menstrual bleeding for at least one (1) year prior to initial dosing. Menopause will be confirmed by a plasma FSH level of >20 IU/L at screening.

Women are considered post-menopausal and not of child bearing potential if they have had 12 months of natural (spontaneous) amenorrhea with an appropriate clinical profile (e.g. age appropriate, history of vasomotor symptoms) or have had surgical bilateral oophorectomy (with or without hysterectomy), total hysterectomy or tubal ligation at least six weeks ago. In the case of oophorectomy alone, only when the reproductive status of the woman has been confirmed by follow up hormone level assessment is she considered not of child bearing potential.

All female patients of childbearing potential must have negative pregnancy test results at Screening and Baseline visits.

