8.6.7 Pregnancy

Pregnancy tests are required of all women of childbearing potential. Female subjects with documented post-menopausal status (as confirmed by FSH > 20 at screening) are not required to be tested for pregnancy.

Serum pregnancy tests will be performed at screening. At all other times urine pregnancy tests may be used.

If a urine pregnancy test is performed and is found to be positive, this will require immediate performing a serum β -hCG test. If positive, the Sponsor and Investigator will decide if discontinuation from the trial is required or whether study assessments can continue without compromising the patient's safety.

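### Table 8-1 footnote 3 ties the urine pregnancy tests after Visit 1 to FSH ≤ 20 alone, contradicting Section 8.6.7, which exempts only women with documented menopause

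*Protocol*

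**What the plan says.** Four places in the protocol bear on who has a pregnancy test and when.

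- **Section 8.1, Table 8-1, footnote 3.** FSH and a serum pregnancy test are done at Visit 1 in female subjects. After that: "all other visits pregnancy test in urine (if FSH ≤ 20". The FSH value is the whole condition. FSH is scheduled once, at Visit 1.
- **Section 8.6.7.** The rule is "Pregnancy tests are required of all women of childbearing potential". The only exemption is: "Female subjects with documented post-menopausal status (as confirmed by FSH > 20 at screening) are not required to be tested for pregnancy".
- **Section 4.1, criterion 14.** The definition reads "Women are considered post-menopausal and not of child bearing potential if they have had 12 months of natural (spontaneous) amenorrhea", together with an appropriate clinical profile; qualifying surgery is the alternative. Natural menopause is to be confirmed by a screening FSH above 20 IU/L. The criterion also states: "All female patients of childbearing potential must have negative pregnancy test results at Screening and Baseline visits".
- **Section 8.6, opening text.** Safety assessments are specified in its subsections, and the assessment schedule gives their timing.

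The SAP does not address pregnancy testing.

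**The concern.** Sections 4.1 and 8.6.7 treat FSH as confirmation of a menopause already established from the bleeding history. The footnote makes it the sole test. Because footnote 3 asks for FSH in female subjects generally, and not only in those reporting amenorrhea, women who still menstruate will also have an FSH value to which the cut-off can be applied. One screening value would then govern every later visit.

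Scheduled testing is how an unrecognised pregnancy would be found before the next infusion. Section 9.7 says that there are no reproductive toxicity data for the drug, and Sections 7.2 and 9.7 both require study drug to stop if a subject becomes pregnant. A missed test in a woman who can conceive could prolong fetal exposure. Nothing in the efficacy or safety analysis depends on this.

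**Working it through.** The plan gives no figure to reproduce. The check compares the rules case by case and then counts the visits concerned.

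**Who is tested after Visit 1**

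| Woman | Footnote 3, read literally | Sections 4.1 and 8.6.7 | Agreement |
|---|---|---|---|
| (a) FSH ≤ 20, of childbearing potential | Tested | Tested | Yes |
| (b) FSH > 20, 12 months' natural amenorrhea with a fitting clinical profile | Not tested | Exempt | Yes |
| (c) FSH > 20, menopause not documented, not surgically sterile | Not tested | Tested | **No** |
| (d) FSH ≤ 20, surgically sterile (for example hysterectomy) | Tested | Not of childbearing potential under 4.1 | No, but harmless over-testing |

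Only case (c) leaves a woman who could become pregnant untested.

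**How many tests are at stake in case (c)**

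1. The pregnancy-test row of Table 8-1 marks 16 visits: 1, 2, 101 to 106, 199, 201 to 206 and 299. Count: 1 + 1 + 6 + 1 + 6 + 1 = 16. This agrees with the footnote's reference to all other visits, so the count does not rest on the extracted table alone.
2. Remove Visit 1. The serum test there carries no FSH condition: 16 − 1 = 15.
3. Remove Visit 2 (Baseline). Criterion 14 requires a negative test there, and Section 4 adds: "Deviation from any eligibility criterion excludes a subject from enrollment into the study, and randomization to study treatment". A woman of childbearing potential cannot properly be randomized without that test, whatever the footnote says: 15 − 1 = 14.
4. The 14 comprise 7 dosing visits (Days 1, 15, 29, 57, 85, 113, 141, matching the infusion days in the protocol summary) and 7 later visits (Days 169, 197, 225, 253, 281, 309, 337): 7 + 7 = 14.
5. Criterion 14 requires highly effective contraception through dosing and on to study completion. All 14 visits, Day 1 to Day 337, lie inside that period.

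**Which text should prevail**

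Section 8.6 gives the content of each safety assessment to its subsections and the timing to the schedule. On that division 8.6.7 decides who is tested and the Table 8-1 row decides at which visits. Read that way, the woman in case (c) is tested at all of them. The footnote departs from the division by adding its own condition on who is tested, and that condition differs from the one in 8.6.7.

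**The case against.** The strongest reply is that the protocol already resolves the matter. By Section 8.6 the schedule governs timing only. Section 8.6.7 is unambiguous, and the bracket in the footnote is probably shorthand for the similar bracket in 8.6.7, with the menopause condition left out. Several safeguards also remain: the Visit 1 serum test, the Baseline test enforced through eligibility, and highly effective contraception until study completion. The Site Operations Manual, which is not available here, may make the rule plain to sites. All of this stands and limits the harm. It does not remove the contradiction. Section 8.1 directs sites to the schedule for each visit, and that is where the incomplete condition sits.

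Three stronger readings are tempting, and the documents do not support them.

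- *The protocol leaves these women untested.* It does not: 8.6.7 requires their tests. The gap arises only where a site applies the footnote in isolation.
- *Section 4.1 itself states a testing exemption.* It supplies the definition of childbearing potential and the Screening and Baseline requirement. Only 8.6.7 states an exemption.
- *Tests up to 14 weeks after the last dose matter and later ones do not.* Section 7.2 does say that certain patients "must be reminded not to become pregnant for 14 weeks after the last dose of study medication", but it addresses those who discontinue the study. For those who remain, contraception runs to study completion, so the 14 visits should not be split at that point.

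**Conclusion.** The inconsistency is real and minor. Footnote 3 states a rule for urine pregnancy tests that conflicts with Section 8.6.7 for one group: women with a screening FSH above 20 who are not post-menopausal under Section 4.1. For each such woman, a site following the footnote literally would omit up to 14 post-Baseline tests.

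The finding that the texts conflict is firm, because footnote 3 is shown in full and nothing is redacted from it. Any consequence in practice is uncertain. It assumes that such a woman is enrolled and that her site gates testing on FSH alone, and the documents establish neither. The number affected cannot be derived and may be zero. The statistical analysis is unaffected.

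**What to change.** In footnote 3, replace the bracketed FSH condition with: *for all women of childbearing potential as defined in Section 4.1; not required in women with documented post-menopausal status confirmed by FSH > 20 at screening (Section 8.6.7)*.

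This brings the schedule into line with 8.6.7 and also removes the unnecessary testing in case (d). The cost is one footnote edit at the next amendment, plus at most 15 urine tests per affected woman: 1 at Baseline, which criterion 14 already requires, and the 14 later ones, which 8.6.7 and the schedule already call for. Women correctly classified as post-menopausal face no added burden.
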